### Statistical criteria to terminate the trial

There are no statistical criteria for stopping the trial early; as the intervention is considered low risk. Decisions to stop the trial early on grounds of safety or futility will be made by the Trial Steering Committee or funding body on the basis of advice from the DMEC.

### Procedure for accounting for missing data

The primary analysis will be an intention-to-treat (ITT) analysis with participants with complete SF-36 data at six months post-randomisation. A sensitivity analysis will be undertaken to impute missing SF-36 and EQ-5D data using baseline and follow-up data from the group of patients with valid data from both measures at six-month post-randomisation. As this is an ITT analysis, withdrawals and protocol violations will be analysed in their groups as randomised.

### Analysis of primary objective

As the trial is a pragmatic randomised, with a usual (control) treatment arm, data will be reported and presented according to the revised CONSORT 2010 statement (Schultz et al, 2010). The statistical analysis will be performed on an intention-to-treat-basis.

All statistical exploratory tests will be two-tailed with  $\alpha = 0.05$ . Baseline demographic (age, gender) and person reported outcome measures (PROM) data (SF-36, PHQ-9, EQ-5D, GSE, de Jong Loneliness Scale, 6CIT) will be assessed for comparability between the groups.

The aim of the analysis will be to establish firstly whether there are benefits from a telephone friendship intervention compared with the control group. Since the intervention, the telephone friendship group, is a group or therapist based intervention, there may be clustering or correlation of the participants' outcomes within a telephone befriending group. Therefore to make allowance for this the primary analysis will compare mean SF-36 Mental Health dimension scores at six months between the intervention group and control group using a marginal general linear model (GLM), with robust standard errors, and an exchangeable correlation (Walters, 2009). The marginal model will use Generalised Estimating equations (GEE) to estimate the regression coefficients. Participants in the control group will be treated as clusters of size one in the analysis. The exchangeable correlation assumes that participant outcomes within each cluster (telephone befriending group) have the same correlation. A 95% confidence interval (CI) for the treatment group coefficient, the difference in SF-36 mental health dimension scores between the intervention and control group, will also be calculated. An adjusted analysis will also be performed alongside this unadjusted analysis which will include baseline covariates, such as age, gender and baseline SF-36 mental health score in the marginal general linear model.

For the primary outcome, the SF-36 Mental Health dimension score at six months follow-up, missing data will be imputed through a variety of methods, including Last Observation Carried Forward (LOCF), regression and multiple imputations.

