## 9. Statistics

### Sample Size

For the purposes of sample size estimation the primary outcome will be the mean SF-36 mental health (MH) dimension score at six-months post randomisation. The SF-36 mental health dimension is scored on a 0 (poor) to 100 (good health) scale. A previous general population survey of Sheffield residents has demonstrated that the SF-36 can successfully be used as an outcome measure for community dwelling residents aged 75 or more where a response rate of 82% was achieved (Walters et al 2001). From this general population survey of 3,084 Sheffield community residents, the mean SF-36 mental health score was 68.3 with a standard deviation of 19.9 (Walters et al 2001).

The developers of the SF-36 have suggested that differences between groups of between 5 and 10 points on the 100-point scale can be regarded as “clinically and socially relevant” (Ware et al 1993). If we assume a standard deviation of 20 points for the SF-36 Mental health score at six months post randomisation and that a mean difference in MH scores between the intervention and control group of 8 or more points is the smallest difference that can be regarded as clinically and practically important. We are going to analyse the six-month outcome data with a multiple regression/analysis of covariance model (ANCOVA) model with baseline score as a covariate. We shall assume a correlation of 0.50 between the baseline and six-month mental health score. Then to have an 90% power of detecting this 8-point mean difference in MH scores at six months between the Intervention and controls as statistically significant at the 5% (two-sided) level will require 99 patients per group (2 x 99 = 198 in total).

However, the telephone befriending intervention is a group or facilitator-led intervention. Therefore the success of the intervention may depend on the facilitator delivering it so that the outcomes of the participants in the same group with the same facilitator may be clustered. If we assume an average cluster size of 6 subjects per telephone befriending group and an intra cluster correlation (ICC) of 0.04, then the design effect is 1.28. With these assumptions and 99 subjects per group the power of the analysis is reduced to 80% to detect a mean difference of eight points in six-month MH scores. If 20% of participants drop out and are lost to follow-up then we will need to recruit and randomise 124 per group (248 in total).

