### 10.2 Fidelity assessment sub-study (facilitators)

The fidelity assessment will assess how well the telephone friendship intervention is delivered according to the intervention protocol (see Section 7). An intervention fidelity framework based on that identified by the Behaviour Change Consortium (Bellg et al, 2005) has been developed (Table 1). The framework sets out the parameters by which quality and fidelity will be measured according to study design, training, delivery, receipt and enactment.

Facilitator attendance at facilitator training sessions will be monitored by a **training attendance register** (not submitted to REC) taken by a single trainer ([name], Community Network) who will train all facilitators to measure 'treatment dose'. The trial manager (RG-W) and content expert (MC) will observe a sample of training sessions (at least one per cycle) and use a **training content checklist** (not submitted to REC) to assure consistency of materials and practice by the trainer as well as to confirm facilitator skill acquisition.

Attendance at group befriending sessions will be monitored by the use of **participant attendance registers** (not submitted to REC) taken by the facilitators at every session during both the one-to-one and group phases.

A random sample of thirteen (5%) audio recordings of group sessions will be taken. Permission to audio record group sessions will be obtained via the **Participant Consent Form (7)** and again at the start of a group session that has been selected. The trial manager (RG-W) and content expert (MC) will use a **facilitator checklist** (not submitted to REC) to assess:

- The match with the intervention protocol, in terms of the content and techniques delivered;
- The extent to which facilitators have enabled choice and decision-making;
- “Drift” in facilitation skills and intervention delivery (for those facilitating groups across successive waves / cycles) with information on adherence being fed back to facilitators as necessary.

The group facilitation skills of individual volunteer facilitators will be self-assessed, with facilitators recording any difficulties with the delivery of the intervention protocol in a **facilitator diary** (not submitted to REC).

The **General Perceived Self Efficacy (GSE) Scale (11)** and **de Jong Gierveld Loneliness Scale (12)** will be used to test the extent to which baseline loneliness and self-efficacy affect all outcomes at follow-up.

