**Table 1. Fidelity assessment strategies**

Goal	Description	Strategies
Design		
Comparable treatment dose	Adequate description of the intervention dose to ensure that variation in dose is recorded.	
 
Set minimum/maximum number of one-to-one telephone contacts
 
Set minimum/maximum duration of one-to-one telephone contacts
 
Set frequency of one-to-one telephone contacts
 
Set minimum/maximum number of group telephone contacts
 
Set minimum/maximum duration of group telephone contacts
 
Set frequency of group telephone contacts
 
A feasibility phase within the design
 

Minimise the risk to implementation	Plan for foreseeable setbacks to successful implementation	
 
A number of recruitment strategies
 
Three recruitment cycles helping to match capacity with recruitment
 
Alternative provider of telephone conferencing technology
 
Alternative sources for the recruitment of volunteers (facilitators)
 

Training		
Standardised training	Attendance Use of standardised materials (and same trainer) Use of standardised practice	
 
Register by Trainer
 
Observed by Trial Manager
 
Content checklist used by Trial Manager & Content Expert on a sample of sessions
 

Provider skill acquisition		
 
Observed by Trial manager
 
Content checklist used by Trial Manager & Content Expert on a sample of sessions
 

Minimise "drift" in skills/delivery (if facilitators are working across three cycles)	Adherence to training content/delivery techniques	
 
Content checklist used by Trial Manager & Content Expert on a sample of sessions (during recruitment cycle 2 and 3 delivery)
 

Delivery		

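### The primary GEE fixes the telephone group as its cluster, so correlation between groups led by the same facilitator would be ignored if facilitators lead more than one group

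*Protocol*

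**What the plan says.** Protocol section 9, Analysis of primary objective, compares six-month SF-36 mental health scores with a marginal linear model fitted by GEE, using robust standard errors and an exchangeable working correlation. Each control participant is a cluster of one. In the intervention arm the cluster is the telephone group: "The exchangeable correlation assumes that participant outcomes within each cluster (telephone befriending group) have the same correlation". The secondary outcomes use the same type of model.

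The Sample Size text of section 9 explains why clustering is expected: "the success of the intervention may depend on the facilitator delivering it". It then places the correlation among people who share both a group and a facilitator, and takes six people per group with an ICC of 0.04.

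Section 10.2 plans checks on drift in facilitation skills "for those facilitating groups across successive waves / cycles". Table 1 repeats the condition: "if facilitators are working across three cycles". The Intervention text of section 1 expects about 24 volunteers to be retained over three recruitment cycles. The number of groups per facilitator is not given.

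**The concern.** GEE robust standard errors need clusters that are independent of one another. If outcomes depend partly on the volunteer, two groups led by the same volunteer share that influence, even in different waves. Treating them as separate clusters leaves their covariance out of the intervention-arm variance. The confidence interval and p-value for the primary comparison would then be too optimistic, increasingly so with more reuse of facilitators. The same applies to the secondary outcomes.

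**Working it through.** **The plan's own figures.** Inputs from Sample Size: "90% power of detecting this 8-point mean difference in MH scores at six months"; "we assume a standard deviation of 20 points for the SF-36 Mental health score"; "We shall assume a correlation of 0.50 between the baseline and six-month mental health score". The ANCOVA residual SD is 20 × √(1 − 0.50²) = 17.32. Then n = 2 × [17.32 × (1.960 + 1.282) / 8]² = 98.5, rounded up to 99, which reproduces the protocol: "statistically significant at the 5% (two-sided) level will require 99 patients per group". With the stated design effect of 1.28, power at 99 per arm is 81.9%, close to the stated 80%. 99 / 0.8 gives 124 per arm. The design effect for groups of six at ICC 0.04 is 1 + 5 × 0.04 = 1.20, not 1.28. That is a separate matter; it matters here only because 1.28 with groups of six implies an ICC of 0.28 / 5 = 0.056, used below as the upper value.

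**Number of groups.** 99 / 6 ≈ 17 groups among those analysed and 124 / 6 ≈ 21 among those randomised, against about 24 volunteers. Three groups per facilitator corresponds to 21 / 3 = 7 facilitators working in all three cycles.

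**Effect of the cluster definition alone.** Assume k groups of six per facilitator, equal arms, singleton controls, and all the ICC at facilitator level. In units of σ²/n, the variance of the difference is 2 + (6k − 1) × ICC. Clustering on group estimates 2 + 5 × ICC. The ratio of the reported to the true standard error is √[(2 + 5 ICC) / (2 + (6k − 1) ICC)]. For k = 2 and ICC 0.04 this is √(2.20 / 2.44) = 0.950; for k = 3 it is √(2.20 / 2.68) = 0.906.

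| ICC | k = 2: SE ratio (implied type I) | k = 3: SE ratio (implied type I) |
|---|---|---|
| 0.02 | 0.973 (5.7%) | 0.947 (6.3%) |
| 0.04 | 0.950 (6.3%) | 0.906 (7.6%) |
| 0.056 | 0.934 (6.7%) | 0.879 (8.5%) |

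The standard error is therefore about 3–12% too small over this range. For k = 1 the ratio is 1.

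**Simulation including small-sample bias.** 40,000 null trials per setting, 99 per arm, 17 groups, total ICC 0.04, unadjusted difference in means, normal critical value. The correction is of Mancl–DeRouen type. Entries are type I error (%) at nominal 5%.

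| Groups per facilitator | Where the ICC lies | Group, plain | Group, corrected | Facilitator, plain | Facilitator, corrected |
|---|---|---|---|---|---|
| 1 | facilitator | 6.0 | 5.2 | 6.0 | 5.2 |
| 2 | facilitator | 7.4 | 6.4 | 7.1 | 5.5 |
| 2 | split 0.02/0.02 | 6.7 | 5.8 | 6.9 | 5.4 |
| 2 | group | 6.0 | 5.2 | 7.0 | 5.5 |
| 3 | facilitator | 8.9 | 7.7 | 8.4 | 5.9 |
| 3 | split 0.02/0.02 | 7.3 | 6.4 | 7.9 | 5.5 |
| 3 | group | 6.0 | 5.2 | 7.6 | 5.4 |

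**Second simulation.** With 21 groups of six, 20% loss, ICC 0.04 all at facilitator level and group clustering with an uncorrected sandwich, type I error was 6.0%, 6.7%, 6.4% and 8.3% for 21, 14, 11 and 7 facilitators. With the ICC split evenly it was 5.6–6.7%. Facilitator clusters with a leverage-corrected sandwich and Satterthwaite t gave 4.8–5.5% in every setting.

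**The case against.** A reader might infer that the protocol names the facilitator as the sole source of clustering and then contradicts itself. It does not. Both parts of section 9 name group and facilitator (or therapist) together, both place the correlation within the telephone group, and the design effect uses group size.

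A reader might also infer that the standard errors are too small as planned. That needs two things the protocol does not assert: facilitators who lead several groups, and correlation that carries across their groups. The passages on reuse are conditional, and about 24 volunteers for 17–21 groups makes one group each possible. If all the correlation sits at group level, the planned clustering stays near 6% whatever the reuse. The three-groups-each case is the far end of what Table 1 allows, not an expectation. On the other side, section 1 speaks of those volunteers who choose to facilitate groups, so 24 may be an upper figure, and a shortage of volunteers is a named risk.

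Finally, it is tempting to say that the plan uses an uncorrected sandwich estimator. The protocol says only that the errors are robust. A small-sample correction is commonly left to the statistical analysis plan, which is not shown, so its absence is not a fault here. Without reuse its omission would cost about one percentage point.

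These limits stand. What survives is that the protocol fixes the group as the cluster while allowing for facilitators who span waves.

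**Conclusion.** The point holds conditionally. If some facilitators lead two or three groups and a facilitator effect exists, the fixed cluster definition omits part of the variance and makes the standard error about 3–12% too small (ICC 0.02–0.056, all at facilitator level). At ICC 0.04 with an uncorrected sandwich, type I error is about 6% with no reuse, 6–7.5% with two groups per facilitator and 6.5–9% with three; the spread reflects the split of the ICC and the simulation set-up. Groups per facilitator, the ICC split and the uncorrected variance are all assumptions. The inflation is modest, but it bears on the primary comparison, its conditions are foreseeable, and it is cheap to guard against.

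**What to change.** In section 9, for both the primary and the secondary outcomes, define the intervention-arm cluster as the facilitator, so that all groups led by one volunteer form one cluster. Controls stay as singletons. If every facilitator leads one group, the clusters are the same as now.

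Pair this with a small-sample-corrected robust variance and Satterthwaite-type degrees of freedom. The pairing is essential: re-clustering without a correction gave 6.9–8.4% in the first simulation where a facilitator effect was shared across groups. The correction and the reference distribution should be chosen together, since Mancl–DeRouen with t on clusters minus one was over-conservative at 2–4% in one check.

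The costs are a slightly wider confidence interval, a change to the analysis code, and recording a facilitator identifier for each group and linking it to the analysis dataset. Section 10.2 says that facilitators take the attendance registers, but not that the registers record who led the group, so this needs to be confirmed. The definition should be settled before outcomes are compared by arm.

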**SAMPLE SIZE:** A sample size of 99 participants for each trial arm achieves an 80% power to detect an eight-point difference in mean SF-36 MH scores at 6 months follow-up between the intervention and control groups. Taking into account participant drop out (20%), we will need to randomise 124 subjects to each arm (248 in total).

**PLANNED ANALYSES:** The aim of the analysis will be to establish firstly whether there are benefits from the intervention compared with the control group. Mean QoL scores at 6 months (primary outcome) and 12 months (secondary outcome) will be compared using a marginal general linear model which will include baseline covariates. Ninety-five percent confidence intervals will be reported for the mean difference in scores. We will use data collected at study visits plus standard costs and valuation sources to estimate costs and QALYs (via the EQ5D). We will produce cost-utility analyses from a NHS /social care perspective and a wider societal perspective. Cost-effectiveness will be described using cost-effectiveness acceptability curves.

**PROJECT TIMETABLE:** Months 1-7: study set up (obtain approvals, convene local implementation groups, agree service provision with charities, recruit and train research assistants, launch recruitment, recruit Trial Steering Committee; Months 8-9: participant recruitment of first wave; Month 11: Intervention delivery starts; Months 13-14 participant recruitment of second wave; Month 18 interim assessment of feasibility; Months 19-20 complete recruitment; Months 17-36 follow up; Months 36-38 data cleaning, analysis, write up, dissemination.

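### The protocol contradicts itself on whether the primary model adjusts for baseline; if the unadjusted model governs, power at 99 per arm falls below the stated 80%

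*Protocol*

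**What the plan says.** Four places in the protocol bear on the primary model.

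- **Section 9, Analysis of primary objective.** The primary analysis compares six-month SF-36 Mental Health means between arms by a marginal general linear model fitted by GEE, with robust standard errors and an exchangeable correlation. Each control participant counts as a cluster of one. No covariates are listed. The section then adds: "An adjusted analysis will also be performed alongside this unadjusted analysis which will include baseline covariates, such as age, gender and baseline SF-36".
- **Section 9, Sample Size.** "We are going to analyse the six-month outcome data with a multiple regression/analysis of covariance model (ANCOVA) model with baseline score as a covariate". The assumed correlation between baseline and six-month scores is 0.50. After allowing for clustering, the section says: "With these assumptions and 99 subjects per group the power of the analysis is reduced to 80" per cent.
- **Trial Summary, Planned Analyses.** Mean scores at six months, identified there as the primary outcome, "will be compared using a marginal general linear model which will include baseline covariates".
- **Section 3, Stopping rules.** The pilot data are used to recalculate the sample size. The inputs are the standard deviation, the intracluster correlation and the correlation between baseline and six-month scores; a correlation below 0.50 is one of the conditions for an increase.

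Only the protocol was available for this review. A statistical analysis plan may exist, but it was not seen.

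**The concern.** In the analysis section, the reference to an unadjusted analysis can only mean the primary comparison just described, so the adjusted model becomes an accompaniment. The other three places assume adjustment. The re-estimation rule is telling: the baseline correlation affects the required sample size only if the model uses the baseline score.

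Two things are at stake. First, two estimates could each be defended from the protocol as the primary result, and they can fall on different sides of 0.05. Second, an analysis that follows the analysis section is not the one for which the trial was sized. A later analysis plan would either inherit an under-powered primary model or depart from the protocol's analysis section.

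**Working it through.** **Inputs, all from Section 9.**
- Difference: 8 points ("a mean difference in MH scores between the intervention and control group of 8 or more points").
- SD: 20 ("If we assume a standard deviation of 20 points for the SF-36 Mental health score at six months post randomisation").
- Correlation r = 0.50.
- Power before clustering: "Then to have an 90% power of detecting this 8-point mean difference in MH scores at six months".
- Level and size: "statistically significant at the 5% (two-sided) level will require 99 patients per group".
- Clustering: average group size 6, ICC 0.04, stated design effect 1.28.
- Loss to follow-up: 20%.

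**Step 1: reproduce the plan's figure.** Under ANCOVA the residual variance is 20² × (1 − 0.50²) = 300.

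n per arm = 2 × 300 × (1.96 + 1.2816)² / 8² = 98.5, so 99. This matches. For loss to follow-up, 99 / 0.8 = 123.75, so 124. This also matches.

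Without the baseline covariate the variance is 400, and 90% power needs 132 per arm. The 99 therefore depends on the adjustment.

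**Step 2: the design effect.** 1 + (6 − 1) × 0.04 = 1.20. The stated 1.28 corresponds to a group size of 8, since 1 + 7 × 0.04 = 1.28. This is a separate discrepancy, so both values are carried through.

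**Step 3: power of each model at 99 per arm.** SE = √[variance × (DE intervention + DE control) / 99] and power = Φ(8/SE − 1.96). The same design effect is assumed for both models.

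| Clustering | Unadjusted (variance 400): SE, power | Adjusted (variance 300): SE, power |
|---|---|---|
| None | 2.84, 80.4% | 2.46, 90.1% |
| 1.20, intervention arm only | 2.98, 76.5% | 2.58, 87.3% |
| 1.28, intervention arm only | 3.04, 75.0% | 2.63, 86.1% |
| 1.20, both arms | 3.11, 72.9% | 2.70, 84.3% |
| 1.28, both arms | 3.22, 70.1% | 2.79, 81.9% |

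The intervention-arm-only rows match the analysis section, where controls are not clustered. The last row is the like-for-like comparison with the sample-size section: its 81.9% is the adjusted figure closest to the stated 80%. A noncentral t calculation lowers the clustered unadjusted range only slightly, to 69.7 to 76.1%.

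**Step 4: precision.** The ratio of standard errors is 1/√0.75 = 1.155, so the unadjusted interval is about 15% wider.

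**Step 5: size needed for 80% power without adjustment.** n per arm = 400 × (DE intervention + DE control) × (1.96 + 0.8416)² / 64.
- 1.20, intervention arm only: 107.9 analysed; 107.9 / 0.8 = 134.9, so 135 randomised per arm (270 in total).
- 1.28, intervention arm only: 111.8 analysed; 111.8 / 0.8 = 139.8, so 140 per arm (280 in total).
- 1.28, both arms: 125.6 analysed; 125.6 / 0.8 = 157.0, so 157 per arm (314 in total).

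The plan is 124 per arm (248 in total).

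**The case against.** A reader might infer that the protocol has settled on an unadjusted primary analysis and that the trial is simply under-powered at about 70 to 77%. The documents do not support that. Three of the four places describe or presuppose adjustment, and if they govern there is no shortfall. The loss of power is conditional on the analysis section prevailing.

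The 70% figure also needs care. It pairs the unadjusted model with a design effect of 1.28 in both arms, whereas the analysis section treats controls as unclustered, and 1.28 does not follow from the stated group size and ICC. For the model that the analysis section describes, 75.0 to 76.5% is the right range, which is 3.5 to 5 points short of 80%. The 70% is valid only as a comparison on the sample-size section's own terms.

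Two other strong readings fail. The baseline score is not discarded, because an adjusted analysis is prespecified alongside. And under randomisation, leaving baseline out does not bias the comparison; the cost is in precision and in uncertainty over which result is primary.

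All of these limits stand. None removes the contradiction, and a separate analysis plan would not remove it from the protocol.

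**Conclusion.** The point holds as a contradiction about the primary model with a conditional loss of power. With an SD of 20, a correlation of 0.50, an 8-point difference and 99 analysed per arm, the unadjusted model misses the stated 80% in every clustered scenario examined. The adjusted model meets it in every one, at about 82 to 87%.

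The size of the gap depends on the assumed correlation of 0.50, and a different correlation in the trial would change it. The planned 248 is adequate for the adjusted model on the protocol's own assumptions, so the calculation is not a case for recruiting more participants.

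**What to change.** In Section 9, Analysis of primary objective, name the GEE marginal model adjusted for baseline SF-36 Mental Health score as the single primary analysis, and label the unadjusted model supportive. This brings the section into line with the Trial Summary, the sample-size section and the re-estimation rule, none of which needs to change on this point.

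The sample size used the baseline score only. Whether age and gender also enter the model, and how the secondary outcomes are modelled, can be fixed in the statistical analysis plan.

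The cost is a short edit to one section. Baseline SF-36 is already collected before randomisation (Section 8), so no new data or participants are needed.
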